### **TIMING OF EVALUATIONS**

**Screening I/II:** all screening evaluations to determine eligibility must be completed within 30 days prior to study entry.

**Entry:** evaluations must occur within 30 days after screening evaluations. If subject shows up ill with any acute symptom, the visit will be postponed until all symptoms resolved for at least 7 days.

**On-Study Evaluations:** study visits must be scheduled on the weeks indicated in the schedule of events +/- 14 days.

**Premature study discontinuation:** Subjects who stop study will undergo the premature study discontinuation evaluations as outlined in the Schedule of events under Week 24 visit. However if subjects stop study medication at any point during the study they will be asked to remain on study and continue to follow the procedures outlined.

### **DETAILED STUDY PROCEDURES BY VISITS**

**Screening I/II:** Before they enter, patients will be asked to visit the clinic at least once to be screened and ensure that they meet the requirements for entry into the study. Screening may take place on the same day as a normally scheduled clinic appointment, as long as subject is fasting. Before any tests can be obtained as part of this study, patients would have to decide whether or not they would like to participate in this study.

- If they choose to enroll, the informed consent form will be signed. The site investigator or a member of the study team will conduct the consenting process and a checklist indicating date and time the consent was signed, who was present, version date and if a copy was provided to participant will be filed in the subjects chart
- A targeted physical examination will be performed including height, weight and blood pressure
- Recent blood work will be reviewed to be sure that they meet the inclusion criteria. The HIV-1 RNA, and HIV testing to confirm HIV status will be obtained from the clinical chart as these are a part of routine care.
- Blood will be drawn for hematology/chemistries and zinc
- Plasma, serum, urine and stool will be collected and stored for potential future testing.
- For woman of reproductive potential, a urine sample will be taken for a pregnancy test.

If a participant does not meet inclusion criteria it will be noted in the chart with the reason for ineligibility.

If a participant meets the inclusion criteria and chooses to enroll, randomization will occur at the entry visit. The study team will notify the pharmacist who will allocate them to one of the two interventions according to the randomization schedule. Participants should start the intervention within two days of randomization allocation.

**Study Entry:** For entry visit, this will be fasting, as defined by no food or drink, except for plain water and medications for at least 8 hours. The following procedures will be done at entry.

- A medical history including family history
- Targeted physical exam including weight and blood pressure
- Patients will fill out a dietary, physical activity, and a substance questionnaire.
- Blood, urine and stool will be obtained for markers of inflammation, microbial translocation, oxidative markers, glucose and insulin, chemistries, hematology, lipids and zinc. HIV-1 RNA, and CD4 count will be obtained from the clinical chart as these are part of routine care. Some of the plasma, serum urine and stool will be stored for potential future testing such as additional tests for inflammation, cardiovascular markers, endothelial function markers, oxidative markers. These blood samples will be batched and the tests will be done at the end of the study and are part of this study.
- For woman of reproductive potential, a urine sample will be taken for a pregnancy test.
- CVD Risk Score
- Endothelial function (EndoPAT): a non-invasive, user-independent technique using the FDA-approved EndoPAT2000 (Itamar Medical Ltd, Israel) provides a reliable and reproducible assessment of endothelial function that predicts atherosclerosis and CVD events. Using modified plethysmographic biosensors, the PAT signal is measured from the fingertip by measuring arterial pulsatile volume changes. A cuff is inflated around the upper arm to obstruct flow and released. The surge of blood flow causes endothelial dependent FMD, manifested as a reactive hyperemia. The EndoPAT® calculate the RHI, the ratio of digital pulse volume during reactive hyperemia and the baseline. In addition to the RHI, we will obtain peripheral Aix, adjusted for HR of 75. We have excellent track record in performing vascular studies, and carefully control for factors that could influence endoPAT; studies are performed at 24 C with the patient resting quietly. Subjects will be fasting, without smoking, caffeine, and exercise for >4 hours. Follow-up studies are completed at the same time of day as the initial study using the same equipment.
- Skin AGE levels will be evaluated by a Reader AGE machine. A small area (0.2 cm^2) on the underside of the forearm will be shaved with a safety razor and shave cream if the participant presents with excess hair (this may cause irritation). The area will then be cleaned with an alcohol pad. The subject's arm will be placed in an arm rest for stabilization and the skin area will be scanned with the AGE Reader. The results of the scan will be documented on the study data collection sheets and/or subject research record. In order to measure skin AGEs the instrument used in the study is an investigational device that illuminates a small area of the forearm using skin autofluorescence with UV LEDs. The resulting skin fluorescence is measured over a 60 second period.

Cognivue Test: At each visit you will be asked to answer a series of questions to measure your brain's ability to think, make decisions, detect differences between things, movement skills, remembering things and other skills using a computer monitor with a small wheel that you turn to indicate your answers. This test takes about 10 - 30 minutes to complete. Changes in how your brain works can be due to many things; some of these are being looked at in this study. The results of this test will not be provided to you because the test is not a routine clinical test and no change in your treatment will result.

**Week 6 and 18:**

- Questionnaires about symptoms or any change in health status
- A short targeted physical exam including weight and blood pressure
- Urine pregnancy test for women
- Assess compliance/safety monitoring
- Blood will be collected for hematology/chemistries. HIV-1 RNA and CD4 count will be obtained from the clinical chart, if available.
- Plasma, serum, urine will be collected and stored for potential future testing

**Week 12 and 24:**

- Targeted physical exam including weight and blood pressure
- Assess compliance/safety monitoring
- Questionnaire about symptoms or any change in health status, substance use and physical activity
- Dietary assessment
- Urine pregnancy test for women
- CVD Risk Score
- EndoPAT testing
- Skin AGE measure
- Blood, urine and stool will be collected for hematology/chemistries, lipids, insulin and zinc
- Plasma, serum, urine and stool will be stored for batch testing (similar to baseline visit) to check for inflammation markers, oxidative markers, and markers of gut epithelial destruction and microbial translocation. HIV-1 RNA and CD4 count will be obtained from the clinical chart.
- Cognivue assessment (week 24 only)

-At visits Entry, week 6, 12 and week 18 study medication will be dispensed by the study staff. Subjects will be asked to return all study medication at each visit and the remaining medication will be counted by the study team and returned to the investigational pharmacy. The study team will assess adherence and record in source document. Adherence will be calculated based on the number of pills dispensed and returned. Study staff will also note in the source document if patients report missed doses. Once a patient arrives at their scheduled visit, the study team will fax a prescription to the Investigational pharmacy who will receive the elemental zinc medication/placebo in bulk and dispense per patient when they arrive at their scheduled visit.

- The zinc will be purchased from a certified Compounding Pharmacy. It will be delivered directly to our investigational pharmacy at University Hospitals. The pharmacy will store the zinc according to their regular procedures, and will dispense study drugs at the time of each study follow up visits, and the number of dispensed pills will be based on the randomization arm.

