**Intervention and Duration:**

The duration of the study will be 24 weeks. Patients will be given zinc gluconate capsules at a dose of 90 mg elemental zinc daily or matching placebo for 24 weeks. No additional follow up will occur after 24 weeks.

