**Sample size and population:**

The total sample size is 95 patients, 63 patients will be randomized to two 45 mg (or 90 mg) capsules of zinc gluconate and 32 patients will receive two matching capsules of placebo drug. This study will be conducted at the University Hospitals Cleveland Medical Center. Recruitment will be done at the Special Immunology Unit (SIU) at the University Hospitals Main Campus.

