### **STUDY DESIGN**

This is a double-blind randomized placebo-controlled trial, studying zinc supplementation to prevent HIV comorbidities that are linked to inflammation in subjects  $\geq 18$  years old HIV-infected patients, on stable ART (for at least 12 weeks) and with zinc levels  $\leq 0.75$  mg/L in the last 60 days. The duration of the study will be 24 weeks. The total sample size is 95 patients (n=62 on active and 31 on placebo). Patients will be randomized 2:1 to zinc gluconate tablets at a dose of 90 mg elemental zinc daily or matching placebo. For this confirmatory phase of the randomized trial, we propose twice the number of subjects in the treatment arm compared to the placebo arm from the context of feasibility, resource allocation or logistics, ethical point of view, and risk-benefit ratio. We propose to measure a number of inflammatory and immune activation biomarkers. From our prior experiences with these biomarker distributions, we may find more variability (may include outliers) in some of the response variables (biomarkers) in the treatment arm than the variability in the response variables in the placebo arm. To reduce the impact of such variability in estimating the effect sizes, having more subjects in the treatment arm should lead to more precise estimates, and hence more powerful statistical inferences. Study drugs will be provided free of charge to study participants for the duration of their participation in the study. Antiretroviral therapy will not be provided by the study. The decision for ART changes or discontinuation will be left to the primary care provider, but these changes will be documented in the study chart and will be taken into account during the analyses.

Subjects will be evaluated and data will be collected according to the following schedule:

Evaluation (Weeks)	Screen I	Screen II	Entry	6	12	18	24
Family history of CVD and diabetes		X					X
Framingham and Reynolds Risk Scores			X		X		X
Targeted physical, blood pressure, weight		X	X	X	X	X	X
Anthropometric Measurements	X	X					X
Compliance, safety monitoring				X	X	X	
Smoking, illicit drugs and alcohol status	X				X		X
Dietary and Activity status	X				X		X
Height	X						
Hematology/chemistries	X	X	X	X	X	X	X
Urine $\beta$ -HCG (women)	X	X	X	X	X	X	X
Lipoprotein profile			X		X		X

Insulin, glucose, HOMA-IR			X	X		X
Inflammation and immune activation markers			X	X		X
Gut integrity, microbial translocation, intestinal permeability			X	X		X

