#### Randomization:

The randomization schedule will be performed by a statistician using SAS software to create a list based on permuted variably sized block randomization with block sizes of 6 to generate 50 allocated numbers in two arms. The randomization schedule will be generated by the statisticians prior to the start of the trial by and provided to the investigational pharmacy. After being provided to the pharmacists, the randomization schedule will be maintained in a locked, secured location at the pharmacy. Only site pharmacists can access the randomization schedule at the time of the intervention assignment.

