#### Blinding:

Patients, study staff, and the study statistician will be blinded to treatment allocation (zinc gluconate or placebo capsules).

The research staff as well as the principle investigator will remain blinded to treatment assignment. The research staff will be responsible to prepare DSMP reports with the principal investigator and will include enrollment and dropout rates, protocol deviations, subjects symptoms, review of clinical, laboratory results and percent adherence to treatment, while remaining blinded to treatment allocation.

The principle investigator, as well as the DSMB board will remain blinded throughout the conduct of the clinical trial unless unblinding is warranted to optimize management of an adverse event or for other safety reasons. This will occur in a private location to ensure the rest of the team remains blinded.

All statistical analyses will also be done in a blinded fashion. Data will be exported to the statistician as arm A versus arm B by the research nurse to preserve blinding. For analyzing adherence, they will also only have access to the percent as opposed to pill counts the research nurse uses to calculate this.

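### The dispensing instruction ties the number of pills to treatment arm. This contradicts two matching capsules per arm and, if followed literally, would let the blinded study team infer allocation.

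*Combined protocol and SAP*

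**What the plan says.** All references are to the combined protocol and SAP.

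- **Dispensing rule.** Under Detailed Study Procedures by Visits, the closing item of Week 12 and 24 covers how the pharmacy stores and supplies the product. It ends by saying that "the number of dispensed pills will be based on the randomization arm".
- **Units per arm.** Sample Size and Population says that "63 patients will be randomized to two 45 mg (or 90 mg) capsules of zinc gluconate" and that "32 patients will receive two matching capsules of placebo drug".
- **Dose levels.** Intervention and Duration describes "zinc gluconate capsules at a dose of 90 mg elemental zinc daily or matching placebo for 24 weeks". Study Design agrees on a single dose level: "Patients will be randomized 2:1 to zinc gluconate tablets at a dose of 90 mg elemental zinc daily or matching placebo".
- **Who handles the units.** Study staff give out medication at Entry and at weeks 6, 12 and 18. Returns are brought to each visit, where "the remaining medication will be counted by the study team". Adherence is then worked out from the units supplied and the units brought back (Week 12 and 24).
- **Who is blinded.** The Blinding section covers patients, study staff and the statistician. On adherence data it says of the statistician that "they will also only have access to the percent as opposed to pill counts the research nurse uses to calculate this".
- **Who knows the allocation.** The Randomization section restricts the schedule to the site pharmacists.

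**The concern.** In a two-arm trial with one dose level and a matching placebo, allocation should decide what is in the capsule and nothing else that can be seen. A rule that makes the count depend on arm gives the arms a visible difference, and it does so at the step where blinded staff must know the count in order to calculate adherence. The sentence is an operating instruction about what the pharmacy will supply, and the pharmacy holds the allocation list, so it could be carried out as written.

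At stake is the blinding of the people who record adherence, ask about symptoms and help judge whether an event is related to the study product. Tolerability and the proportion of participants with higher-grade related events form a secondary endpoint, and safety is part of a primary objective.

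**Working it through.** The plan gives no figure to reproduce on this point. The check compares the statements and adds simple arithmetic.

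**1. Does the described regimen allow the count to differ by arm?**

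| Source | Zinc | Placebo |
|---|---|---|
| Sample Size and Population | two capsules | two matching capsules |
| Intervention and Duration; Study Design | one dose level | matching |
| Week 12 and 24, last item | number depends on arm | number depends on arm |

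The first two rows give equal counts and the third says otherwise. The strength wording in the first row is unclear: 2 × 45 mg = 90 mg, while 2 × 90 mg = 180 mg against a stated 90 mg daily. That ambiguity concerns strength and does not affect this comparison, because the number is two on either reading.

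**2. What count follows from two capsules in each arm?** Sample Size and Population does not say how often the two capsules are taken. Assume they are the daily intake, since the dose is stated per day elsewhere.

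- Per nominal dispensing interval: 6 weeks × 7 = 42 days, and 2 × 42 = 84 capsules.
- Over the study: 24 weeks × 7 = 168 days, and 2 × 168 = 336 capsules, which equals 4 dispensing visits × 84.

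Both figures are the same for zinc and placebo, so a dispensed count would carry no information about allocation.

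**3. What could staff infer if the last item were applied literally?** The adherence calculation requires the team to know the dispensed number for each participant. Two systematically different numbers would split participants into two groups. The allocation is 2:1, and the Randomization section specifies "permuted variably sized block randomization with block sizes of 6". A complete block of 6 therefore holds 6 × 2/3 = 4 zinc and 6 × 1/3 = 2 placebo participants. The commoner count would point to zinc, without access to the schedule.

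**4. Does the Blinding section close this route?** It withholds counts from the statistician only. The research nurse, who is meant to stay blinded, still works with them. The same nurse exports the data under the labels A and B, so arm-dependent counts would also show which label is zinc.

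**5. Which outcomes depend on judgement by these staff?**

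- *More exposed:* adherence; attribution of adverse events to study product (Study Endpoints, secondary); and the discretionary decision to interrupt study product for a related Grade 2 toxicity (Toxicity Management).
- *Less exposed:* the co-primary laboratory measures. The inflammation and translocation markers are stored and assayed in batches. Analysis is by intention to treat, so a biased adherence record would not change who is analysed.

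**The case against.** The strongest reply is that this is a drafting slip. One dose level against matching placebo gives no reason for unequal counts, the clause states no per-arm numbers, and it stands alone. The revision summary says the document was updated to add a further study phase, and other text looks unharmonised: capsules in one section and tablets in another, unclear strength wording, and 50 allocation numbers for a trial of 95. The author may simply have meant that the arm determines which product is supplied. This is plausible and cannot be excluded, but the benign reading requires setting aside the word number in a dispensing instruction, and no other section corrects it. The reply limits the consequence and leaves the contradiction in place.

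Three stronger readings are tempting, and the documents do not support them.

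- *That patients would be unblinded.* Each patient sees only their own supply. Nothing describes patients being told the count for each arm or comparing supplies.
- *That the plan itself admits counts reveal the arm.* Withholding counts from the statistician, in the section on blinding, suggests the authors saw a possible risk. It may be only a precaution, and the section never says that counts differ.
- *That the sponsor chose unequal dispensing.* Nothing shows such a decision.

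**Conclusion.** The inconsistency is established: the dispensing clause cannot be squared with two matching capsules in each arm, with a single dose level against matching placebo, or with the blinding of study staff. The loss of blinding is conditional. It arises only if the clause is carried out as written, and then only the staff route is supported by the text. In that case it could reach any participant, because units are handed out at four visits and returns are counted afterwards. That describes reach and is not an estimate of bias. The likely damage is to adherence assessment and to adverse-event attribution, with little effect on the batched biomarkers.

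The 84 and 336 capsule figures assume that two capsules is the daily intake and that visits fall on their nominal weeks. The contradiction itself needs neither assumption. The point should be corrected because the clause is operative and the remedy costs almost nothing. It does not show that the trial has been run unblinded.

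**What to change.** Reconcile Sample Size and Population, Blinding, and the last item of Week 12 and 24:

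1. Remove or correct the clause so that allocation determines only which product, zinc or placebo, is dispensed.
2. State that the number and appearance of units dispensed at each visit do not depend on allocation.
3. Confirm that the pharmacy's written instructions say the same.

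The unclear strength wording and the alternation between capsules and tablets should be made consistent in the same edit. Which strength or number of units is correct is for the sponsor to state.

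If both arms already receive the same number of units, the cost is one sentence in the protocol and a check of the pharmacy instructions. If they do not, the sponsor needs to establish who could see the counts before describing the trial as double-blind.

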### **TOXICITY MANAGEMENT**

Only toxicities related to study drugs (zinc) will be considered. Toxicities felt to be unrelated to study drugs will be left to the discretion of the primary care provider of the study participants. AACTG grading system will be used for evaluation for Grading Adult Adverse Experiences.

-Subjects who develop a new Grade 1 adverse event or toxicity may continue study drug without alteration of the dosage. Subjects experiencing Grade 1 adverse event who choose to withdraw from the study should be encouraged to complete the study evaluations as outlined in the Schedule of events.

- For all toxicities of Grade 2 thought to be related to the study drug, the study medication can be held at the discretion of the local investigator. If unable to resume it within 3 weeks, then the subject will be taken off study drugs but will continue to be followed and undergo the evaluations as per schedule of events.

- For all toxicities Grade 3 thought to be related to study drug, study medication will be held until the toxicity grade returns to  $\leq$  Grade 2 or to the entry value. If unable to resume study drugs for longer than 3 weeks, then the subject will be taken off study drugs but will continue to be followed and undergo the evaluations as per schedule of events.

- For any Grade 4 toxicity (confirmed  $\geq$  2 values for laboratory abnormalities) regardless of the cause, subjects will be taken off study drugs but will continue to be followed and undergo the evaluations as per schedule of events. Exceptions are asymptomatic elevation of indirect bilirubin in subjects receiving indinavir or atazanavir therapy, asymptomatic elevation of CPK, or elevations in lipid levels.

### **CRITERIA FOR PERMANENT STUDY DISCONTINUATION:**

-Request by the subject to withdraw

-At the discretion of the IRB

-Pregnancy or breast-feeding

-Request of the primary care physician if s/he thinks the study is no longer in the best interest of the subject.

